Active-for-Life (Active-Life) with COPD is a 10-week intervention designed to increase total PA with an emphasis on increasing the time spent in LPA and decreasing sedentary time. Key components of Active-Life include (a) a laboratory-based exercise program comprised of functional circuit training (FCT), walking and stretching which can easily be transitioned to the home setting with minimal equipment; (b) a behavioral component with a structured self-efficacy enhancing intervention that includes self-regulation strategies; and (c) an education component that addresses the distinct health benefits of LPA and MVPA, the negative consequences of too much sedentary time, and an action plan for dealing with acute exacerbations of COPD.

The objective is to systematically test the efficacy of our Active-Life intervention and examine theoretically-based mediators of PA outcomes for people with COPD. Our central hypothesis is that Active-Life will have positive, lasting effects on objectively measured PA and on other indicators of frailty. Active-Life integrates PA into daily life and establishes a goal for subjects: to increase total PA, combined LPA and MVPA, by at least 60 minutes a day. This far exceeds the effects of other published PA interventions for people with COPD^{23,38} and, if successful, will advance PA science in clinically important ways. The Active-Life program was developed by [name] and her research team through a series of preliminary studies; its feasibility is well established and preliminary data are promising. Outcomes will be measured at baseline; at the end of the 10-week intervention; and at 3, 6, and 12 months after the end of the Active-Life intervention. The primary dependent variables are objectively measured PA and sedentary behavior. Secondary outcome variables are frailty indicators.

Aim 1. Determine the short term (end of 10 week intervention) and sustained effects (1 year follow-up) of the Active-Life intervention vs a program of chair exercises plus health education (Chair-HE, *active control*) on PA and sedentary behavior. The working hypothesis for this aim, based on preliminary data, is that the Active-Life group will significantly increase time spent in PA (combined LPA and MVPA) and decrease time spent in sedentary behavior compared to the active control group and that these effects will be sustained at 3, 6, and 12 months after completion of the 10 week Active-Life intervention.

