Significant benefits can be accrued by a lifestyle that includes a higher volume of LPA on a regular basis.^{15,31,32,34,46,47} Growing evidence suggests that increasing LPA and decreasing sedentary time provides health benefits *independent of the amount of MVPA performed*.^{48,49} A recent review of prospective studies also demonstrated that, *independent of total PA*, too much sedentary behavior (sitting and screen time) was associated with cardiovascular mortality.⁵⁰ Other benefits of increasing LPA include reduced risk of mortality³⁰ and metabolic syndrome,³¹⁻³³ attenuation of arterial stiffening in old age,³⁴ reduced risk of hospital admission for COPD,^{13,14} and delay in the onset of frailty.⁴⁷ Even LPAs such as standing are important: greater time spent standing is associated with a decrease in all-cause mortality, including cardiovascular disease mortality.³⁰ The volume of LPA required to accrue health benefits is not known, but evidence suggests that replacing 30 minutes of sedentary time with LPA has the potential to improve physical health as indicated by body mass index, number of health conditions, number of medications, lower-body physical function, and general health rating.⁵¹ However, most people with COPD do not understand the importance of increasing LPA and decreasing sedentary time.

Promoting PA in COPD. Pulmonary rehabilitation, which includes exercises and health education, increases exercise capacity and health related quality of life. However, it has not been very effective in increasing levels of PA,^{3,22,23,52,53} possibly because (a) it does not adequately address the behavioral issues associated with many decades of habitual inactivity and (b) it focuses on MVPA that may be too strenuous and not feasible for long-term maintenance in people with COPD. Few pulmonary rehabilitation programs employ theory-based behavioral interventions to change PA behavior and none have focused on increasing LPA.

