Active-Life development. The 10-week Active-Life intervention was designed by [name] and her team to focus on LPA as a more realistic target for people with moderate to very severe COPD. Additional refinements include: (a) the addition of pedometers to provide objective day-to-day feedback, (b) the addition of SMART goals and implementation intentions to facilitate the accomplishment of PA goals, (c) refinement of PA education to establish the importance of LPA and the negative effects of too much sedentary behavior, and (d) phone coaching to facilitate the transition from laboratory to home and long term maintenance.

In the early phase of pilot testing we compared the effects of a 6-week intervention to the same intervention delivered over 10 weeks. All subjects indicated that a 6-week program was too short and they recommended a 10- or 14-week program. The majority recommended 10 weeks.

Active-Life pilot. We pilot tested the 10-week Active-Life intervention in 10 subjects and the observed changes in PA behavior are promising (see Figure 2). Physical activity was measured with ActivPAL and ActiGraph GT3X accelerometers. ActivPAL measures the time spent in PA (standing and stepping) 24 hours/day and the ActiGraph measures the intensity of PA during waking hours.

ActivPAL data demonstrated that subjects increased their total PA time at the end of the intervention by a mean of 60 (SD=78) min/day and 80% of the gains were maintained at 2-month follow-up. Repeated measures ANOVA demonstrated significant increases in the time spent in total PA ($P = 0.029$). A similar improvement was seen for the time spent sitting/lying (sedentary time).

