1. Boosters sessions are scheduled concurrently with the testing sessions at weeks 22 and 34. This is to

minimize the number of trips that subjects make to the laboratory.

2. The booster session is an intervention session that is the same as the intervention sessions during weeks 1-10. These sessions are designed to support people in their efforts to be physically active, to help them remember how to do the exercises and to get them re-energized about being physically active.
3. Each booster sessions takes approximately 2 hours. Since the booster will be combined with testing visits the total time will be 4 hours (booster = 2 and testing = 2).

Measures for Aim 1. The primary dependent variables are the time spent in PA and sedentary behavior. ActivPAL data will be used for hypothesis testing and ActiGraph data will be used to describe the intensity of PA. PA will be measured for 7 consecutive days at each measurement.

A substantial body of literature supports the reliability and validity of the ActivPAL.^{126,127} The *ActivPAL3 accelerometer* will be used to measure the time spent standing/stepping and sitting/lying. The ActivPAL3 accelerometer is a small (15g) rectangular device (53 x 35 x 7 mm) taped to the anterior aspect of the thigh. The sampling frequency is 10 Hz and the recording interval is 0.1 second. The proprietary software classifies free-living activity into time spent lying/sitting, standing and stepping. ActivPAL is waterproofed by wrapping it in a barrier film that does not have to be removed for bathing. First applied in the laboratory, it is then worn 24 hours a day for a 7-day period to capture each measurement, and then removed in the laboratory. This greatly reduces the loss of data that occurs when subjects wear a monitor during waking hours but forget to put it on when they wake up each morning. In our pilot work we have had no missing ActiPAL data. We will report time spent sitting/lying, time spent standing/stepping (separately and combined) and the number of transitions from sitting to standing per day. Time spent standing and stepping and sitting/lying will be used for hypothesis testing (Aim 1).

Complimentary measures of PA.

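### On complete, untransformed 24-hour ActivPAL days, Aim 1's sedentary outcome is 1440 minutes minus its PA outcome: it is not separate evidence, and it includes sleep

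*Combined protocol and SAP*

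**What the plan says.** Under Measures for Aim 1 the protocol states: "The primary dependent variables are the time spent in PA and sedentary behavior". The same section settles the device: "ActivPAL data will be used for hypothesis testing and ActiGraph data will be used to describe the intensity of PA". On wear, the ActivPAL is first applied in the laboratory and "it is then worn 24 hours a day for a 7-day period to capture each measurement". On classification: "The proprietary software classifies free-living activity into time spent lying/sitting, standing and stepping". The variables to be tested are then given: "Time spent standing and stepping and sitting/lying will be used for hypothesis testing (Aim 1").

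The Active-Life pilot paragraph treats standing and stepping together as PA, and equates sitting/lying with sedentary time: "A similar improvement was seen for the time spent sitting/lying (sedentary time").

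The Aim 1 hypothesis in the Specific Aims is two-part. Active-Life is to increase combined PA and "decrease time spent in sedentary behavior compared to the active control group". The Data Analysis Plan applies ANCOVA at 10 weeks and at 3, 6 and 12 months, adjusted for baseline PA and other covariates, and claims effectiveness at p < 0.05.

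No section gives a sleep log, a waking window or any rule that takes sleep out of the ActivPAL record. Only the ActiGraph is limited to waking hours, and it is descriptive.

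**The concern.** Three classes that fill a fixed 1440-minute day leave no room for two free outcomes once two of the classes are added together. If PA is standing plus stepping, sitting/lying is whatever is left. A fall in sedentary time is then the same fact as a rise in PA, and a reader who sees both reported as significant may take them as two pieces of evidence.

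The second issue is what the variable measures. A person asleep is lying down, so the night falls in the same class as daytime sitting. A shift between sleep and daytime sitting leaves the 24-hour total unchanged. Reducing sedentary time is half of the paradigm set out in the Specific Aims, so a primary variable that adds nothing to PA and mixes in sleep serves that aim poorly.

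**Working it through.** **The plan's own figure.** The only sample-size calculation concerns the mediators. With γ = 0.26, ρ = 0.3 and unit variances, two-sided α = 0.05 and 80% power give 7.849 / (0.0676 × 0.91) = 127.6, so 128; and 128 / 0.7 = 182.9, so 183. Both reproduce, and neither depends on the present point.

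**Identity.** On a complete day:

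- sitting/lying + standing + stepping = 24 × 60 = 1440 min
- PA = standing + stepping
- Sed = 1440 − PA, at baseline and at every follow-up

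**ANCOVA.** Let PA at follow-up = a + b·arm + c·PA at baseline + error. Substituting PA = 1440 − Sed on both sides gives Sed at follow-up = a′ − b·arm + c·Sed at baseline − error. The arm coefficient changes sign; the residual variance, standard error and p-value do not. Keeping baseline PA as the covariate gives the same result, because 1440 − PA and PA span the same space once an intercept is present. Further covariates change nothing, provided both models use the same ones.

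**Numerical check.** 2000 simulated trials used 64 per arm and the pilot change SD of 78 min/day. The baseline mean of 300, baseline SD of 100 and effect of 30 min/day are assumptions. The largest difference in size of estimate, SE or p-value was about 10⁻¹², and no trial disagreed at p < 0.05. One of these datasets gave +21.69 (SE 12.86, p = 0.094) for PA and −21.69 (SE 12.86, p = 0.094) for sitting/lying.

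**Number of tests.** 2 outcomes × 4 time points = 8 apparent tests; 8 / 2 = 4 distinct ones.

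**Sleep.** The documents give no sleep figure. Assuming 7–9 h, 420–540 of the 1440 minutes are sleep and fall in sitting/lying. Removing them gives waking Sed = 1440 − PA − sleep, so the arm effect is −(effect on PA) − (effect on sleep).

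**Redundancy left after removing sleep.** If sleep varies independently of PA, r = −SD(PA) / √(SD(PA)² + SD(sleep)²). The sleep SDs and the PA SD of 100 are assumptions; 78 is the pilot change SD.

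| Sleep SD (min) | Levels, PA SD 100 | Changes, PA SD 78 (simulated) |
|---|---|---|
| 30 | −100/√10900 = −0.96 | −0.93 |
| 60 | −100/√13600 = −0.86 | −0.79 |
| 90 | −100/√18100 = −0.74 | −0.66 |

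In the simulations of change, the PA and waking-sedentary tests disagreed at p < 0.05 in 13%, 24% and 35% of trials, against 0% without sleep removal.

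**The case against.** **The identity is conditional.** This stands. It needs complete records, the same days for both variables, and no separate transformations. The plan gives no ActivPAL valid-day rule, and the Data Analysis Plan allows transformations; with separate log transforms, about 22% of the simulated trials disagreed at p < 0.05. That would be an artefact of scale, since both variables still carry the same information. Standing or stepping tested alone is not an exact complement, but the Aim 1 hypothesis concerns combined PA. Continuous wear is prescribed and the pilot had no missing ActivPAL data, so the conditions are close to what the plan expects.

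**The harm is limited.** This also stands. A reader might infer that counting the result twice raises the false-positive rate. It does not: a duplicate test adds no further chance of error. The PA outcome is untouched. If sleep does not differ by arm, the waking and 24-hour definitions estimate the same effect, and the waking version adds noise.

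**Stronger readings that the documents do not support.**

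- That the trial cannot say whether waking sedentary time falls. The raw record can be scored for a waking window; what is missing is the rule.
- That the protocol contradicts its own definition when it writes "too much sedentary behavior (sitting and screen time"). That phrase describes the exposure in a cited review. The protocol's operational term is sitting/lying.
- That the sponsor will report two confirmed effects. Table 5 lists both variables under one primary-outcome heading, and no section calls them independent evidence.
- That the pilot's improvement in sedentary time was nothing but this identity. The identity predicts such a result, but no sedentary values are printed to check.

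**Conclusion.** The point holds as one of interpretation and construct. Followed as written, with complete days and untransformed data, the plan tests one quantity under two names: the correlation is −1, the p-values are identical, and there are four distinct tests where eight appear. This follows from the definitions and does not depend on effect size or sample size. That sleep is included is an inference from 24-hour wear, a lying/sitting class and the absence of any removal rule; the documents do not say it in words.

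A significant decrease in 24-hour sitting/lying should therefore not be read as evidence beyond the PA result, nor as a measure of waking sedentary time. Because it concerns the definition of a primary outcome, the matter should be settled before the arms are compared.

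**What to change.** **Preferred.** In Measures for Aim 1, define the sedentary outcome as sitting/lying during waking hours. Fix the waking window by a prespecified scoring rule on data already collected: the main overnight lying bout in the ActivPAL record, optionally cross-checked against ActiGraph waking wear. Report 24-hour sitting/lying as description only. The ActiGraph should serve only as a check, since the pilot section says its wear time is less consistent.

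**Otherwise.** Name combined standing plus stepping as the single primary outcome, and state in one sentence that 24-hour sitting/lying is its complement and not a second finding.

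**Cost.** The first option needs a scoring rule and some extra data processing, with no new data collection. Its downside is measurement error in the waking window, and the table above shows that the two outcomes would still be strongly correlated. The second option costs a sentence but gives up a separate test of sedentary time.

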Aim 2. Determine mediating effects of self-efficacy and outcomes expectation on PA and sedentary behavior outcomes of Active-Life. We hypothesize that positive changes in self-efficacy for overcoming barriers to LPA and outcomes expectations for exercise will mediate changes in the time spent in PA and sedentary behavior.

Secondary Aim. Determine short term and sustained effects of Active-Life vs active control on frailty indicators: strength, endurance, balance, walking speed and physical function. The working hypothesis is that the Active-Life group will have significantly higher scores (less frailty) on all frailty indicators after completion of Active-Life compared to the active control group and effects will be sustained at 3, 6 and 12 months.

This research addresses a key issue identified by the 2012 Institute of Medicine report: Living Well With Chronic Disease.³⁹ We will test an intervention to reduce the burden of chronic illness, targeting people with COPD, most of whom have multiple chronic conditions.⁴⁰ The intervention is aimed at physical inactivity, a risk factor for chronic disease. If this intervention is successful in reducing/delaying frailty it could have long reaching economic effects by decreasing health care utilization and the cost of care for people with COPD.

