	Health Education	
 • Includes basic lung physiology, healthy eating, travel issues, common medications, energy conservation, review of CDC PA guidelines, etc.

combined with walking, because walking is a common activity of daily living.

Behavioral: PA-specific self-efficacy enhancing intervention. Self-efficacy is a form of “situation specific self-confidence.” Self-efficacy expectations, which have profound effects on multiple elements of behavior, reflect individuals’ beliefs in their capabilities to successfully meet the challenge at hand. The expectations influence the choice of activities in which people engage, the effort they put forth during the activity, and how long they persist in the activity when faced with difficulties and/or challenges.⁶⁴⁻⁶⁶ Substantial evidence suggests that perceived self-efficacy is an important and consistent determinant of the initiation and maintenance of health-promoting behaviors such as exercise. Those with a high sense of self-efficacy for PA are more likely to engage in PA, work hard at it, and persist despite setbacks. Self-efficacy is especially important during the initial adoption of exercise and PA,⁶⁷ but it also plays a role in the maintenance stage of exercise and PA.^{68,69} [name] and her team developed and tested an exercise-specific self-efficacy enhancing intervention^{70,71} to promote both adherence to upper body resistance training and an active lifestyle that included adherence to national PA guidelines. Results were positive and are described in the preliminary data.⁷² In the current application she modified the intervention to focus on increasing LPA and decreasing sedentary time.

Pedometer. Pedometers are affordable, provide a simple, easy-to-understand output for the user, and provide immediate feedback, which can be motivational.⁷³ When combined with goal setting, pedometer-based interventions have been successful in promoting increased walking.^{74,75} A meta-analysis of studies with older adults reported a moderate effect size, 0.53.⁷⁶

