
Social Cognitive Variables	Δ ^a Standing/Stepping (min./day)	P
Barriers-efficacy for Light PA (baseline)	r = .556	.095
Barriers-efficacy for Light PA (end of intervention)	r = .496	.145
Barriers-efficacy for Light PA (2 mo. follow-up)	r = .515	.128
MOEES (baseline)	r = -.193	.593
MOEES(2 mo. follow-up) ^b	r = -.401	.250

Δ^a = 2-mo. follow-up minus baseline measure; ^bNote data from end of intervention is not available for this measure; BE-PA = barriers-efficacy for physical activity; MOEES = multidimensional outcome expectations for exercise scale.

Figure 3. Timeline for intervention and follow-up boosters

Follow-up = weekly phone coaching for 2 weeks, every other week coaching until 3 months, monthly phone coaching until 6 mo. follow-up.

Summary of Activities

Testing visits	Visit 1	Visit 2	Week 1-10	Week 11	Week 12-21	Week 22	Week 34	Week 62
Screening	X							
Testing visit #1-5		X		X		X	X	X
Activity monitoring (7 days)		X		X		X	X	X
Structured intervention elements			Week 1- 10		Week 11-21	Week 22	Week 34	
Lab-based exercises, with behavioral/ educational program			two visits a week for 8 weeks, then one visit/week for 2 weeks.					
Coaching phone calls (5 minutes)					Total of 8 phone calls during the first 6 months of follow-up.			
Booster session (one full lab-based session)						X*	X*	

Active-Life intervention. Key components are described below and in Table 4. The details of the intervention are documented in a manual for the staff to use, session-by-session, making it easy to implement in a systematic manner (Appendix A section 44.1).

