Barriers-Efficacy for PA. Self-efficacy for overcoming barriers to PA will be measured to document subjects' perceived ability to follow through and continue with PA when faced with common barriers to exercise (*Barriers Efficacy Scale: COPD version*). This is a form of self-regulatory efficacy. The Barriers Efficacy Scale: COPD, which we used in one of our earlier studies of COPD,⁶³ was modified from the well-established barriers efficacy scale published by McAuley.^{134,135} It includes 14 items, 11 original and 3 specific to people with COPD. The reliability and validity of both the original scale and the COPD version are supported.^{71,114,134-137}

Outcome Expectations for PA. The *Multidimensional Outcome Expectations for Exercise Scale (MOEES)* will be used to measure outcome expectations for PA.¹³⁸ The MOEES is constructed of 15 items organized into three subscales (physical, self-evaluative and social). Using data from a large group of older subjects, construct validity was supported by factor analysis and significant associations in the predicted direction for PA and self-efficacy.¹³⁸ Internal consistency reliability was demonstrated for each scale with Crobach's alphas from 0.81 to 0.84.¹³⁸

Table 5. MEASURES	Screen	Base-line	Wk. 2	Wk. 10	Mo. 3, 6	Mo. 12
PRIMARY OUTCOME - PA						
-Time spent in PA and sedentary behavior ActivPAL and ActiGraph monitoring (7 days)		X		X	X	X
HYPOTHEZIZED MEDIATORS			X	X	X	X
-Barriers Efficacy Scale			X	X	X	X
-Multidimensional Outcome Expectations Scale			X	X	X	X
SECONDARY OUTCOMES - FRAILTY INDICATORS						
-6-Minute walk test		X		X	X	X
-Isometric strength (knee flexors & extensors)		X		X	X	X
-PROMIS Physical Function (CAT)		X		X	X	X
-Short Physical Performance Battery		X		X	X	X
OTHER FACTORS THAT INFLUENCE PA (COVARIATES)						
Symptoms						
Chronic Respiratory Disease Questionnaire -SA		X		X	X	X
PROMIS Fatigue(CAT)		X		X	X	X
Negative Affect			X		X	X
PROMIS Anxiety (CAT)		X		X	X	X
PROMIS Depression (CAT)		X		X	X	X
Historical PA		X				
Historical PA Questionnaire						
Social Support for PA						
Positive and Negative Social Influences on PA in Older Adults (PNSIPA)		X		X	X	X
Self-Regulation of PA			X		X	X
PA self-regulation scale (PASR12)						
Measures used to describe the sample						
-Functional Comorbidity index	X					
-Frequency of acute exacerbations over the past year (**since enrollment)	X			X**		X
-Spirometry	X					

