Measures at week 2 will be taken during the second week of the intervention to give subjects time to establish realistic expectations.						
Measures at week 10 will be taken after completing the 10 week intervention, and measures at 3, 6 and 12 months will be taken at 3, 6, and 12 months after completion of the intervention. Computerized Adaptive Testing (CAT), Chronic Respiratory Questionnaire Self-Administered (CRQ-SA).						

Measures for Secondary Aim. Physical activity is an important frailty indicator. In addition to PA we will measure strength, endurance, physical function, balance and walking speed as indicators of frailty.

Strength and endurance will be measured with two widely used field tests of physical performance: isometric strength and the six-minute walk. All tests will be administered using standardized instruction.

Isometric strength of the knee extensors and flexors will be measured with a hand-held dynamometer (Lafayette Manual Muscle Testing System, Model 01165). The system includes an adjustable strap for stabilization of the limb during testing. Measures will be taken with the leg flexed at 90°, with the subject seated for knee extension and standing for knee flexion. This device uses precise load cell technology for measuring peak force within a 0-300 lb. range with 1% accuracy. Standard testing procedures will be followed, whereby the tester meets the effort of the participant during a 4-6 second maximal voluntary contraction. This is a “make” test, not a “break” test (i.e., there is no attempt to overcome or break the subject’s resistance). Measures taken with hand-held dynamometers are highly reliable and appropriate for measuring change over time.¹³⁹⁻¹⁴¹ Because this device is portable, training and testing subjects in community settings is possible.

Six-minute walk test (6MWT) will be conducted according to the American Thoracic Society guidelines.¹⁴² Support for validity and reliability of the 6MWT is well established.¹⁴³

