standard deviation of the mediator, and ρ was the correlation between the intervention and the mediator. We set type I error rate α at 0.05, type II error rate β at 0.2 (power = 0.8), the residual variance at 1, mediator variance at 1, and correlations between intervention and mediator range from 0.1 to 0.5. The effect size γ was determined using Cohen's definition of effect size from small (0.14) to medium (0.39)¹⁶². Evaluating our previous study, we expected to detect small to medium effect size ($\gamma = 0.26$). Therefore, when the correlation between the intervention variable and mediator was 0.3, we required 128 patients to reach 80% power. Because our past experience indicated 30% attrition, we proposed to enroll 183 patients at baseline to provide enough power to infer intermediate variables.

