Data Analysis Plan. Data on all patients who are randomly assigned to Active-Life intervention group and active control group will be analyzed on an intention-to-treat basis. Deviations from randomized allocation will be reported. Summary statistics will be used to characterize the sample distribution at each time period. Proper transformations will be investigated and taken if the sample distributions violate the normality assumption. For **Aim 1** of determining the Active-Life intervention effect on PA and sedentary behavior at 10 weeks, and 3, 6, and 12 months, Analysis of Covariance (ANCOVA) will be used at each time period to adjust for the baseline PA measurements and other baseline covariates.¹⁶³ The dependent variable for the ANCOVA is PA and sedentary behavior described in the Research Design section. The adjusting covariates include age, gender, COPD severity, and variables listed in the "other factors that influence PA" section. The Active-Life intervention is claimed to be effective if the marginal p -value of the intervention variable is < 0.05 . For **Aim 2** of identifying intermediate variables (or mediators) between the Active-Life intervention and PA, we will calculate the average causal mediation effects (ACME).^{164,165} The potential mediators include variables barriers-efficacy for PA, and outcome expectations for PA. The significant non-zero causal mediation effect indicates that the intervention on the PA goes through the mediator. The analysis will be carried out using the R mediation package.¹⁶⁴ Since we anticipate having missing values at 10 weeks, we plan to deal with them via standard multiple imputations. More specifically, we will run mediation analysis on multiple imputed data sets. A confidence interval is used to summarize the ACME. Finally, since the mediation analysis assumes the sequential ignorability assumption^{161,166} we will evaluate this assumption by conducting sensitivity analysis.

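### Aim 2 has no pre-randomization score for either mediator; the first is taken in week 2 of the intervention, and the analysis plan does not say how that score will be used

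*Combined protocol and SAP*

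**What the plan says.** **Schedule.** In Table 5 the row group headed "HYPOTHEZIZED MEDIATORS" contains the Barriers Efficacy Scale and the MOEES. The heading and both scale rows are marked at week 2, week 10, months 3 and 6, and month 12. Screening and baseline are blank. Physical activity (PA), the frailty indicators and most covariates do have a baseline mark. The footnote gives a reason for the timing: "Measures at week 2 will be taken during the second week of the intervention to give subjects time to establish realistic expectations." Table 5 is the only schedule for the mediators; statements elsewhere that measurement starts at baseline concern the outcomes.

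**Hypothesis.** Specific Aims, Aim 2: "We hypothesize that positive changes in self-efficacy for overcoming barriers to LPA and outcomes expectations for exercise will mediate changes" in PA and sedentary time.

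**Analysis.** The Data Analysis Plan estimates average causal mediation effects (ACME). It does not state which mediator visit enters the models, whether the mediator is a level or a change, or which covariates are used. The remark "Since we anticipate having missing values at 10 weeks" suggests the week-10 value. The plan adds that, "since the mediation analysis assumes the sequential ignorability assumption", a sensitivity analysis will be done. Baseline PA is named as a covariate for Aim 1 only.

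**Sample size.** The Power Analysis is built on the mediator slope: at a correlation of 0.3 between arm and mediator, "we required 128 patients to reach 80% power".

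**The concern.** By week 2, participants have been randomized and have attended roughly 2 to 4 of the 18 laboratory sessions (two per week at that stage). In the Active-Life arm these sessions are meant to raise self-efficacy. The analyst then has two routes, and each has a weakness.

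- **Treat week 2 as the starting value.** If the arms already differ at week 2, a change score or a week-2 covariate subtracts part of the effect under study.
- **Use week 10 alone.** Randomization protects the arm-to-mediator path. It does not protect the mediator-to-PA path. A participant who starts with a high score may score high at week 10 and also become more active for reasons that do not run through the week-10 score. Without a pre-randomization score this cannot be fully separated from mediation.

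At stake is the interpretation of Aim 2, the aim on which the sample size rests.

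**Working it through.** **1. The plan's own figure.** Inputs from the Power Analysis: two-sided α 0.05, power 0.80, slope γ = 0.26, residual and mediator variances 1, arm–mediator correlation ρ = 0.3.

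n = (1.96 + 0.8416)² / (0.26² × (1 − 0.3²)) = 127.6, so 128. Then 128/0.70 = 182.9, so 183. Both stated figures reproduce.

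**2. Scale.** With 1:1 allocation the arm indicator has SD 0.5, so ρ = 0.3 implies an arm difference in the mediator of 0.3/0.5 = 0.60. The within-arm variance is 1 − 0.09 = 0.91 (SD 0.954). The planned ACME is 0.60 × 0.26 = 0.156.

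**3. Week 2 used as the starting value.** Let f be the share of the week-10 arm difference already present at week 2, and r the adjustment slope (r = 1 for a change score). Both are assumed. The ACME becomes 0.156 × (1 − r f).

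| f | r = 0.5 | r = 1.0 |
|---|---|---|
| 0.10 | 0.148 | 0.140 |
| 0.25 | 0.137 | 0.117 |
| 0.50 | 0.117 | 0.078 |

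**4. Week 10 used alone.** Let g be the effect of starting level on later PA that bypasses the week-10 mediator (per SD of starting level), and k the within-arm correlation of starting and week-10 mediator. The documents give neither.

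- No baseline adjustment: bias = g k / 0.954.
- Baseline PA adjusted, with an assumed correlation of 0.5 with starting level: bias = 0.75 g k / [0.954 (1 − 0.25 k²)].
- Baseline mediator adjusted, measured with reliability λ: bias = (1 − λ) g k / [0.954 (1 − λ k²)]. The value λ = 0.82 is assumed, within the 0.81–0.84 alphas quoted for the MOEES subscales; λ = 0.6 is an assumed pessimistic value for ratings made before exposure.

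| g, k | none | baseline PA | baseline mediator, λ = 0.82 | λ = 0.6 |
|---|---|---|---|---|
| 0.1, 0.5 | 0.052 | 0.042 | 0.012 | 0.025 |
| 0.2, 0.6 | 0.126 | 0.104 | 0.032 | 0.064 |
| 0.3, 0.7 | 0.220 | 0.188 | 0.066 | 0.125 |

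With an error-free baseline score (λ = 1) the bias is 0. With g = 0 every entry is 0. If the true slope is 0.26, the unadjusted estimate averages 0.26 + 0.052 = 0.31 to 0.26 + 0.220 = 0.48, so the sign does not change.

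**5. Power once the baseline mediator is adjusted for.** If the residual variance does not fall, power = Φ(√[128 × 0.26² × 0.91 × (1 − k²)] − 1.96). This is 0.80 unadjusted, and 0.68, 0.61 and 0.52 at k = 0.5, 0.6 and 0.7. Restoring 80% would need 127.6/(1 − k²) = 170.1, 199.4 or 250.2, that is 171, 200 or 251 evaluable participants.

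**6. Tipping point for the sensitivity analysis.** At the planning values the ACME reaches zero at an error correlation of 0.26 × 0.954 / √(1 + 0.26² × 0.91) = 0.24. The assumed g and k imply g k / √(1 + g²) = 0.05 to 0.20.

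**The case against.** **Week 2 was chosen deliberately.** It was, and the reason is sensible. It supports having a week-2 score; it does not require omitting a baseline one. The pilot collected both scales at baseline (Tables 2 and 3), so this is feasible.

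**The confounding is not demonstrated.** This stands. A reader might infer from the protocol's statement "Those with a high sense of self-efficacy for PA are more likely to engage in PA" that starting efficacy is a confounder. That sentence describes efficacy acting on activity, which is the mediator path itself. It does not say that starting efficacy has a separate, lasting effect. For outcome expectations there is less still: the protocol describes the evidence as mixed, and the pilot MOEES correlations with PA change are negative (−.193 and −.401, N=10). The pilot correlations, including .556 for baseline barriers-efficacy, cannot size the confounding.

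**Some covariate control is foreseen.** This also stands. The Measures text intends the other PA-influencing variables as covariates where suitable, without restricting this to Aim 1. The Preliminary Studies section expects the larger sample to permit control of relevant variables. Neither specifies an Aim 2 model, but the unadjusted column is therefore an upper illustration.

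**A sensitivity analysis is planned.** It shows how much confounding would nullify the ACME. It cannot remove confounding by a variable that was not measured.

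**Adjustment has a price.** It does. Measurement error leaves residual bias, and the loss of power is large enough that the adjusted ACME should not be the only result.

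**Conclusion.** The gap in the schedule is plain: no pre-randomization score exists for either mediator, and the plan does not say which mediator visit, form or covariates Aim 2 uses. Both available routes can distort the ACME, in different ways.

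The size is not known. The illustrative slope bias of 0.05–0.22 (0.04–0.19 with baseline PA adjusted), against a planned 0.26, rests on assumed g of 0.1–0.3 and k of 0.5–0.7; the upper g exceeds the planned mediator effect itself. If starting level acts only through the later mediator, or only through baseline PA that is adjusted for, there is no bias.

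Two stronger readings should be resisted. One is that a positive Aim 2 result would be spurious: the documents do not show the separate effect this needs. The other is that the sponsor intends week 2 as a baseline: the plan is silent on this. Aim 1 is unaffected, and 128 and 183 stand as calculated. This is a worthwhile, inexpensive improvement to Aim 2.

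**What to change.** 1. In Table 5, add the Barriers Efficacy Scale and the MOEES at the existing baseline visit, before randomization. Keep week 2.
2. In the Data Analysis Plan, state that the ACME uses the week-10 mediator adjusted for baseline PA, that week 2 serves neither as a baseline nor as a covariate, and that the ACME is reported both with and without the pre-randomization mediator score.
3. In the Power Analysis, state that the 80% applies to the model without the baseline mediator score, and that the adjusted slope has about 52–68% power at n=128 for k of 0.5–0.7. No increase in sample size is proposed.
4. For participants already enrolled without a baseline score, use the week-10 value adjusted for baseline PA, declare the limitation, and report the error correlation at which the ACME reaches zero (about 0.24 at the planning values).

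**Cost.** Two short questionnaires (14 and 15 items) at a visit where others are already given, and a few sentences of text. Ratings made before exposure may be less realistic and carry measurement error. Under the assumptions above, adjustment removes about 70–77% of the slope bias at reliability 0.82 (for example 1 − 0.066/0.220 = 70%), and about half at 0.6. If there is no separate effect of starting level, the adjustment only costs power, which is why both versions should be reported.
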